10.2 Sample Size Calculations

The target sample size for this study is 30 participants to be randomized and to wear both contact lens types. This target was determined based on the sample size calculation below:

to demonstrate non-inferiority in high contrast binocular distance logMAR visual acuity for the Test contact lens compared with the Control contact lens, the sample size estimation is based upon a one-sided paired t-test with $\alpha = 0.025$, $\beta = 0.200$ and a non-inferiority margin of 0.050 logMAR when postulating a true difference of 0.00 logMAR with a standard deviation of 0.07 logMAR a total of 26 participants is required. The target for this study will be for 30 participants to complete the study without a significant protocol deviation.

Therefore, in this study, a maximum of 40 participants may be randomized to achieve a maximum of 30 completed.

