10.3 Statistical Analysis

Statistical analysis will be undertaken by the study biostatistician. The critical measure for statistical significance is set at alpha = 5% level with a P-value ≤ 0.05 . All subjects who have completed the study will be included in the analysis.

Lens performance will be compared per study design. Descriptive statistics (e.g., mean, standard deviation) and/ or frequency of counts for categorical data may be produced for primary and/or second interests. Paired t-test may be used to compare slit lamp biomicroscopy, contact lens fit and subjective scores between study contact lens types. Where applicable, Repeated Measures Analysis of Variance (ANOVA) or paired analysis may be used to compare the variables between study visits. Binomial tests may be used to analyze the results for the frequencies of subjective and objective preferences.

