11.3 Protocol Deviations

A Protocol Deviation is an instance of failure to follow, intentionally or unintentionally, the requirements of the protocol. Investigators will not deviate from the protocol except to protect the

rights, safety and well-being of human subjects. Under emergency circumstances deviations may proceed without prior approval of the Sponsor and the IRB. Deviations shall be reported to the Sponsor, IRB and the regulatory bodies, as required.

Significant deviations which require changes to the research protocol or informed consent process/document or other corrective actions to protect the safety, welfare, or rights of patients or others must be reported to the IRB/EC within ten business days of the deviation occurring (or its discovery). All deviations shall be reported to the Sponsor within two working days.

All deviations occurring during the study will be documented on a protocol deviation form and documented in the final Clinical Study Report (CSR).

Sponsor contact details **for Protocol Deviations** are:

Contact: Clinical Operations, CooperVision

[REDACTED]
[REDACTED]
[REDACTED]
[REDACTED]

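### The enrolment target counts only completers without a significant deviation, but completers are capped at 30 regardless and all are analysed, so a non-inferiority trial has no per-protocol check

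*Combined protocol and SAP*

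**What the plan says.** Section 10.2 (Sample Size Calculations) sets the target: "The target for this study will be for 30 participants to complete the study without a significant protocol deviation". The sentence after it allows that "a maximum of 40 participants may be randomized to achieve a maximum of 30 completed", with no condition about deviations. Section 7.3 (Subjects) likewise gives a range of 10 to 30 completers, again unconditioned, out of at most 40 enrolled.

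Section 10.3 (Statistical Analysis) has one rule on who is analysed: "All subjects who have completed the study will be included in the analysis". It defines no per-protocol set, no exclusion for deviations and no sensitivity analysis.

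Outside Section 10.2, significant deviations are described only in Section 11.3 (Protocol Deviations), as a class with an IRB reporting deadline: "Significant deviations which require changes to the research protocol or informed consent process/document or other corrective actions to protect the safety". Section 11.3 also requires every deviation to be documented and included in the study report.

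The primary hypothesis (Section 10.1) is non-inferiority of the Test lens in binocular high-contrast distance acuity, with "a non-inferiority margin of 0.050 logMAR" (Section 10.2).

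**The concern.** The number 30 refers to one population where the trial is sized and to another where it is analysed. The rule for stopping at 30 completers cannot be squared with the target once a single completer has a significant deviation. The site and sponsor also have no rule for deciding which deviations count, and nothing requires that decision before the masking codes are opened.

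In a superiority trial, analysing every completer usually works against the sponsor's claim when deviations blur the treatment contrast. In a non-inferiority trial it can work in favour of the claim. If a child was measured in the same lens type at both follow-up visits, the expected Test minus Control difference is zero whatever the true difference. If the two lenses were worn in the wrong order and analysed as assigned, the sign reverses. Either case moves the mean away from a true deficit and makes a false non-inferiority conclusion more likely. With about 30 children, two or three such cases are enough to matter.

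**Working it through.** **The target against the cap.** With at most 30 completers and one deviating completer, the number of clean completers is at most 30 − 1 = 29, below the target of 30. Under Section 10.3 all 30 are analysed.

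**Inputs.** From Section 10.2: "the sample size estimation is based upon a one-sided paired t-test", one-sided alpha 0.025, power 80%, margin 0.05 logMAR, and "postulating a true difference of 0.00 logMAR with a standard deviation of 0.07 logMAR". The text does not say whether 0.07 is the SD of the paired difference; it is taken as such here.

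**The plan's own figure.** The normal approximation gives n = (0.07 × (1.96 + 0.84) / 0.05)² = 15.4, so 16. The noncentral t gives 18. The stated 26 is not reproduced from these inputs. That is a separate matter, and the present point does not rest on it. With SD 0.07 and a true difference of zero, power is 93.8% at n = 26 and 96.6% at n = 30.

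**Effect of deviators on the error rate.** Assume 30 completers including k deviators. The other 30 − k have a mean Test minus Control difference of 0.05 logMAR, exactly at the margin, with SD 0.07. Deviators have mean m. Non-inferiority is declared when (mean − 0.05) / (s / √30) is below −t(0.975; 29 df).

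The expected overall mean is ((30 − k) × 0.05 + k × m) / 30. For k = 2:

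- no contrast (m = 0): 1.40 / 30 = 0.0467
- swapped lenses (m = −0.05): 1.30 / 30 = 0.0433
- half the contrast kept (m = 0.025): 1.45 / 30 = 0.0483
- full contrast (m = 0.05): 0.0500

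The standard error is 0.07 / √30 = 0.0128, so these shifts are not negligible. Simulated rates of false non-inferiority (at least 100,000 trials per setting):

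| Type of deviation | k = 0 | k = 2 | k = 3 |
|---|---|---|---|
| No lens contrast (m = 0) | 2.5% | 4.1% | 5.1% |
| Lenses swapped (m = −0.05) | 2.5% | 5.8% | 8.5% |
| Half the contrast kept (m = 0.025) | 2.5% | 3.3% | 3.7% |
| Noise only (m = 0.05, SD 0.14) | 2.5% | about 2.5% | about 2.5% |
| Worse on Test (m = 0.10) | 2.5% | 1.3% | 0.9% |

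The direction and size depend on the kind of deviation. Zero contrast is not the worst case; swapped lenses are worse. The documents give neither the number nor the type of deviators, so every k and m here is an assumption.

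**The case against.** Several objections have weight.

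- **Replacement.** A reader might infer that deviators are replaced and yet kept in the analysis. No sentence says they are replaced. The target and the allowance of 40 randomized suggest it, but the cap of 30 completers in Sections 7.3 and 10.2 contradicts it. What stands is the contradiction, not a replacement rule.
- **Direction of bias.** A reader might infer that deviators' data generally pull the result towards no difference. The documents do not support that. Acuity at the follow-up visits is measured with the study lens on the eye, so a child with under 2 hours' wear, or with mostly habitual lens wear in the week before, still shows the optical contrast. The protocol itself measures acuity after 15 minutes' settling at dispensing.
- **Opportunity for error.** Unworn Pair 1 lenses are collected and the worn pair is retained before Pair 2 is dispensed (steps 27, 35 and 45), so a child should hold one study pair at a time. That leaves mainly a dispensing or labelling error. Such an error is possible, since unmasked staff over-label the lenses at both dispensing visits (steps 23 and 45), but it should be uncommon.
- **Definition.** Section 11.3 sets an IRB reporting rule. It does not claim to define the term for Section 10.2, so the fair statement is that the term is undefined for analysis.
- **Power.** The target of 30 exceeds the stated 26, and on the stated inputs a few lost participants do not endanger power.

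These points limit the size and certainty of the bias. They do not remove the mismatch between target, cap and analysis population, or supply the missing second analysis. Because all deviations must be documented, the information needed for that analysis will exist.

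**Conclusion.** The point holds as a mismatch in the plan together with a possible, not demonstrated, bias. Sections 7.3, 10.2 and 10.3 do not use the same population, one deviating completer is enough to make the target unreachable under the cap, and a non-inferiority claim rests on a single all-completer analysis. The 4.1% and 5.8% rates for two deviators each assume 30 completers, a paired-difference SD of 0.07, a true deficit equal to the margin, and a deviation that removes or reverses the lens contrast. Milder deviations give about 3.3% or no change, and deviations that hurt the Test lens lower the rate. Since the direction cannot be known in advance, showing the result in both sets is the sensible safeguard. This should be corrected, but it does not by itself invalidate the design.

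**What to change.** 1. In Section 10.3, define before unmasking a per-protocol set: completers with no deviation affecting the primary acuity measurement. At minimum, require the assigned lens at both follow-up visits. State explicitly whether the protocol's 2-hour wear, 7 + 3 day window and wear-time requirements also count.
2. Run the primary comparison against the 0.05 margin in all completers and in this set, and treat a non-inferiority conclusion as robust only if the two agree.
3. Use the same definition for the target in Section 10.2, in place of the undefined term.
4. Reconcile the completer caps in both Section 7.3 and Section 10.2 with that target, keeping the ceiling of 40. Amending only one section would create a new contradiction.

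The cost is a wording change, one extra run of the primary analysis and a slightly smaller second set. If the cap is moved from completers to participants randomized, a few more than 30 may complete, within the existing 40.

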10.3 Statistical Analysis

Statistical analysis will be undertaken by the study biostatistician. The critical measure for statistical significance is set at alpha = 5% level with a P-value ≤ 0.05 . All subjects who have completed the study will be included in the analysis.

Lens performance will be compared per study design. Descriptive statistics (e.g., mean, standard deviation) and/ or frequency of counts for categorical data may be produced for primary and/or second interests. Paired t-test may be used to compare slit lamp biomicroscopy, contact lens fit and subjective scores between study contact lens types. Where applicable, Repeated Measures Analysis of Variance (ANOVA) or paired analysis may be used to compare the variables between study visits. Binomial tests may be used to analyze the results for the frequencies of subjective and objective preferences.

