5.7 Rationale for Benefit-Risk Ratio

The knowledge gained from this feasibility study may lead to important conclusions regarding the ocular response and performance of new contact lens materials and designs. The potential risks for participating in this study are minimal, therefore the benefit-risk ratio is acceptable.

6 Ethics Review / Statement of Compliance

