7.5.6 Study Exit

Exit visual acuity (LIHC) will be recorded with subjective spherocylindrical refraction result from V1-A refraction (OD & OS & OU (logMAR)). An exit biomicroscopy assessment will be conducted including Fl staining, if participant was fitted with study contact lenses at the screen visit or if biomicroscopy was not completed at a concurrent visit after the screening.

After the exit assessments have been completed, the participant and investigator will complete the study exit and remuneration forms. At this time, the participant will be considered as having exited the study.

When a participant exits the study, the study exit form will be completed. Therefore, this form will be completed either at completion of the study, or if the participant is discontinued from the study at another time. A study exit form must be completed for all participants who have taken a study ID number. If in the opinion of the investigator post-follow-up visits are required, the exit form will be completed after the last follow-up visit.

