11	Peripheral (outside central 6mm), non-progressive, non-infectious ulcer	Notify Sponsor as soon as possible, within 5 working days ; IRB reporting as per requirements
12	Symptomatic corneal infiltrative event	
13	Superior epithelial arcuate lesions (SEALs) involving epithelial split	
14	Corneal staining \geq dense coalescent staining up to 2mm in diameter (e.g. moderate, ISO 11980 grade 3)	
15	Corneal neovascularization \geq 1.0mm vessel penetration (e.g. \geq ISO 11980 Grade 2), if 2 grade change from baseline	
16	Any temporary loss of \geq 2 lines BSCVA for \geq 2wks	
17	Any sign and/or symptom for which subject is administered therapeutic treatment or which necessitates discontinuation of lens wear for \geq 2 weeks	
10	Other significant event	
Non-significant Adverse Events		
21	Conjunctivitis (bacterial, viral or allergic)	Notify Sponsor as soon as possible, within 5 working days ; IRB reporting as per requirements
22	Papillary conjunctivitis if \geq mild scattered papillae/follicles approximately 1mm in diameter (e.g. ISO 11980 Grade 2), if 2 grade change from baseline	
23	Asymptomatic corneal infiltrative events	
24	Any sign and/or symptom for which temporary lens discontinuation for $>$ 1 day is recommended (if not already classified)	
20	Other sign and/or symptom warranting classification as a non-significant adverse event	

Normal or adaptive symptoms

Transient symptoms such as end-of-day dryness, contact lens awareness, itching or burning or other discomfort may occur with contact lens wear and may occasionally reduce wearing time. **These are not reported as adverse events unless in the investigator's opinion they are unexpected in nature, severe or have a high rate of occurrence.**

This clinical study will also ascertain satisfaction or preference with subjective attributes such as comfort, vision, or contact lens handling. Responses to these subjective questionnaires will not be considered as Adverse Events.

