8.4 Discontinuation from the Study

A subject's study participation may be discontinued at any time if, in the opinion of the Sponsor or the investigator, it is in the best interest of the subject. All discontinuations will be fully documented on the appropriate study forms and a discontinuation/exit form will be completed.

9 Device Deficiency Reporting

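### Section 10.3 defines no analysis set other than completers, so a subject withdrawn for an ocular reaction drops out of the analysed slit-lamp results for the lens being worn

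*Combined protocol and SAP*

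**What the plan says.** Section 10.3 has one sentence on who is analysed: "All subjects who have completed the study will be included in the analysis". It does not separate performance from safety. Ocular findings come up in the same section: "Paired t-test may be used to compare slit lamp biomicroscopy, contact lens fit and subjective scores between study contact lens types". No safety set, all-exposed set or adverse-event analysis appears elsewhere in the document.

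On leaving early, section 8.4 lets either the sponsor or the investigator withdraw a subject whenever they judge that "it is in the best interest of the subject". Among the significant adverse events in 8.1, code 17 covers "Any sign and/or symptom for which subject is administered therapeutic treatment or which necessitates discontinuation of lens wear for" two weeks or more. On numbers, section 10.2 says that "a maximum of 40 participants may be randomized to achieve a maximum of 30 completed".

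Data on leavers are collected. Section 7.5.6 states: "An exit biomicroscopy assessment will be conducted including Fl staining, if participant was fitted with study contact lenses at the screen visit". It also requires an exit form for every subject given a study ID, including those discontinued. Table 3 schedules slit-lamp and adverse-event assessment at unscheduled visits, and section 8.3 requires a notification form for each adverse event.

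**The concern.** For an ocular-safety outcome, a completer set can select on the outcome itself. A subject whose eye reacts badly may be withdrawn for that reason, and withdrawal then removes the observation from the comparison. A paired test adds a second filter, because it cannot use a subject examined on only one lens.

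At stake is the between-lens slit-lamp comparison of an investigational lens with a marketed control in subjects aged 8 to 18. If one lens leads to more ocular withdrawals, its remaining wearers would look better than all those who wore it. The examinations that would show this are collected, but the plan gives them no place in any analysis by lens.

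**Working it through.** The plan gives no figure for this point. The sample size of 26 in section 10.2 concerns the acuity test and is not used here.

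**1. How many can fall outside the set.** Section 10.2 allows up to 40 randomised and up to 30 completed. With 30 completers, at most 40 − 30 = 10 are outside, and 10/40 = 25%. This comes from recruitment caps and is not a dropout forecast. Two qualifications apply:
- Section 7.3 applies the 40 to enrolment, which 7.5.1 dates from signing the consent forms. On that reading some of the 10 may be screening failures who never wore a lens.
- Section 7.3 accepts as few as 10 completers, so the share could be larger if the study ends short of 30.

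**2. Whether an ocular event can prevent completion.** Each lens is worn for 7 (+3) days, so 10 at most. Part of code 17 is two weeks or more off lenses, which is 14 days. Since 14 > 10, such a subject could not finish that lens period within its window. No passage says that a code 17 event ends participation, so this shows a plausible route and not a rule.

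**3. What happens to each kind of subject under 10.3.**

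| Course | Slit-lamp data held | In the planned comparison? |
|---|---|---|
| Withdrawn on Pair 1, or at Visit 2-A | First lens only | No: not a completer, and no pair |
| Withdrawn on Pair 2 | First lens at Visit 2-A; second lens if examined at exit or unscheduled visit | No: not a completer, even where a pair exists |
| Reaction found at Visit 3-A, study completed | Both lenses | Yes |

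**4. Size of the effect on the slit-lamp mean.** Let 30 completers have mean grade m on one lens, and let k further subjects, withdrawn on that lens for an ocular reaction, have mean grade g at their last examination on it. The mean over these 30 + k subjects is (30m + kg)/(30 + k). It differs from the completer mean by k/(30 + k) × (g − m). The same fraction is the proportion of the 30 + k withdrawn for an ocular reaction. The values of k are assumptions, because the documents give none.

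| k (assumed) | k/(30 + k) | Exact 95% CI for the withdrawal proportion | Shift in mean per grade of excess |
|---|---|---|---|
| 1 | 1/31 = 3.2% | 0.1% to 16.7% | 0.03 |
| 2 | 2/32 = 6.3% | 0.8% to 20.8% | 0.06 |
| 3 | 3/33 = 9.1% | 1.9% to 24.3% | 0.09 |
| 10 | 10/40 = 25.0% | 12.7% to 41.2% | 0.25 |

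The last row is a limit: it needs every place outside the set to be an ocular withdrawal on the same lens. Completers show 0/30 such withdrawals (0% to 11.6%) whatever k is, but that zero is true by definition. The last column bears on the comparison the plan describes.

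**5. Whether another planned analysis fills the gap.** The descriptive statistics in 10.3 are tied to the primary and secondary interests, which 7.1 defines as acuity and subjective vision quality. Section 9.2 commits the study report to a summary of device deficiencies, and 11.3 to documenting deviations. No matching commitment covers adverse events, by lens or overall.

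**The case against.** The strongest reply is that safety is handled outside 10.3 and does not depend on completing. Every adverse event gets a form (8.3) and is followed to resolution (8.2). Serious events go to the sponsor within 24 hours. Leavers fitted with lenses have an exit slit-lamp examination. All of this stands. A reader might infer that adverse events in leavers would be lost or unreported, and the documents do not support that. The gap is in the analysed results only.

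It can also be said that 10.3 includes completers without expressly excluding anyone else, that the slit-lamp t-test is optional, and that no adverse-event analysis is planned for anybody, completer or not. These are fair limits. The completer sentence removes nobody from an adverse-event table, since none is planned. But no second set is defined, and optional wording does not supply the missing summary. The paired test would still drop anyone seen on one lens.

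A reader might take section 5.7 to rest the benefit-risk case on these results. It says only that the study may lead to "important conclusions regarding the ocular response and performance of new contact lens materials and designs", and the sole hypothesis in 10.1 concerns acuity.

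Finally, withdrawals for ocular reactions may be rare over 7 to 10 days in habitual wearers. The only incidence figure in the documents, 0.035% in section 5.2, is for infection alone, so it neither confirms nor rules out withdrawals for lesser reactions.

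**Conclusion.** The point holds for the analysed slit-lamp results. As 10.3 is written, a subject withdrawn for an ocular reaction is left out of the between-lens comparison, and the exit or unscheduled examination enters no planned analysis by lens. The bias is conditional: the comparison could favour one lens if ocular withdrawals are unequal between lenses and those withdrawn had worse grades than those who stayed. One to three such subjects on one lens, against 30 completers, would move that lens's mean by 0.03 to 0.09 of a grade per grade of excess. The cap-based limit is 0.25.

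The documents do not support a claim that the bias favours the Test lens in particular, that it is certain to occur, or that 25% are expected to leave. The primary acuity hypothesis is outside this point. The plan should be changed because the omission follows from its stated rule and the remedy uses data already collected.

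**What to change.** In section 10.3:
- Limit the completer sentence to the acuity and subjective-rating comparisons.
- Define a safety set of all subjects to whom at least one study lens was applied.
- Summarise adverse events, slit-lamp grades (including exit and unscheduled examinations) and discontinuations with reasons by the lens worn at onset or examination. Use the number exposed to that lens as denominator.
- Keep the paired slit-lamp t-test as a supporting analysis. Widening the set alone would not help, because the test still needs both lenses.

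The cost is a few sentences and a few extra descriptive tables, with no new data and no change to any study procedure. One small downside is that denominators will differ slightly between lenses, because a subject who leaves on Pair 1 never wears the other lens.

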13	Study Costs	38
14	Publication Policy	38
15	References.....	39
17	Appendix 1 – [REDACTED]	40
18	Appendix 2 – [REDACTED]	50
19	Appendix 3 – Randomization.....	51
20	Appendix 4 – [REDACTED]	52
21	Appendix 5 – [REDACTED]	65
22	Appendix 6 – [REDACTED]	65
23	[REDACTED] 7 – [REDACTED]	65
24	Appendix 8 – [REDACTED]	65
25	Appendix 9 – [REDACTED]	65

26 Appendix 10 – Adverse Event Case Report Forms	67
27 Appendix 11 – Clinical Trial Product Defect Notification Form.....	70

1 Study Objective

The objective of this Design Validation clinical investigation is to compare the visual clinical performance of the [REDACTED] investigational contact lens to [REDACTED] contact lenses. CooperVision, Inc. (CVI) is aiming to compare visual acuity and subjective vision ratings of vision quality between two CooperVision lenses: [REDACTED] versus [REDACTED] in habitual soft lens wearers. The [REDACTED] lens is a daily disposable investigational lens in this study (as this lens has not been yet approved or commercially available in the US), the [REDACTED] is commercially available in the US for myopia control.

[figure not shown]
[REDACTED] lens is a silicone hydrogel daily disposable (DD) lens with a similar design to [REDACTED] hydrogel DD lenses. CooperVision, Inc. is interested in comparing visual acuity and subjective vision ratings between these two lenses of different materials to gain insight into the differences between these lenses from this aspect.

The primary outcome variable for this study is:

- High contrast, binocular, distance visual acuity (logMAR) at 1-week visit.

The secondary outcome variable is:

- Subjective vision quality (0-100 scale) at 1-week visit

2 Study Design

This will be a prospective, multiple day, double (investigator and subject) masked, randomized, bilateral crossover study comparing a Test lens against an appropriate Control lens. Each subject will wear the Test lens or the Control lens in a bilateral fashion for 7 days (+ 3 days) followed by the alternate lens for 7 days (+ 3 days). The order of lenses will be randomized.

There will be a total of 3 visits in the study as described in Section 7.5 below.

3 Study Devices and Comparator Products

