3.2.2 Other

No other medical devices will be used in this study.

4 Justification for the Study Design

Nonclinical testing methods are not adequate to provide the information needed to advance the development of the ██████████ Contact Lens. A biocompatibility assessment has been completed and the benefit/risk assessment (see Section 5 below) supports the use of the device in this feasibility study. A synopsis of the biocompatibility assessment and prior clinical testing can be found in the Investigator Brochure.

A crossover design has been chosen since it minimizes the impact of potential sympathetic effects between the two eyes (e.g. an uncomfortable lens in one eye may impact the subjective rating of the fellow eye). The study contact lenses do not alter the physiology and hence there is no carryover effect requiring a washout period. The order effect will be tested.

The choice of comparator product was made in order to assess the clinical performance against a currently marketed product representative of generally accepted state of the art.

5 Benefits/Risks of Study Device(s) and Study Procedures

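### The only test named for lens preferences takes no account of the randomised wearing order; if wearers favour the pair worn last, it loses power to detect a real preference

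*Combined protocol and SAP*

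**What the plan says.** The study is a two-period crossover. Section 2 states: "The order of lenses will be randomized". Section 8.1 confirms that preferences are collected: "This clinical study will also ascertain satisfaction or preference with subjective attributes such as comfort, vision, or contact lens handling". Section 7.1 does not list preference as a primary or secondary endpoint.

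The only method named for preferences is in Section 10.3: "Binomial tests may be used to analyze the results for the frequencies of subjective and objective preferences". No order term is mentioned and sidedness is not stated. The same section says "Lens performance will be compared per study design" and sets the analysis population: "All subjects who have completed the study will be included in the analysis".

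Section 4 argues that the lenses do not alter physiology, "hence there is no carryover effect requiring a washout period", and then says "The order effect will be tested". It does not say how, for which outcomes, or what follows from the result.

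Section 7.3 allows 10 to 30 completers. Section 10.2 targets 30, with up to 40 randomised. The randomisation appendix and the appendices that might show the timing, wording and response options of a preference question are redacted or not reproduced. I treat their content as unknown, not as missing from the plan.

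**The concern.** A wearer can compare the two pairs only after wearing both. By then Pair 2 has just been worn, and Pair 1 was removed 7 to 10 days earlier (Table 2). Each wearer gives one comparative answer, so a tendency to favour the last-worn or first-worn pair cannot be separated from the lens effect within that wearer. It can be separated only by comparing the two randomised orders.

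A one-sample binomial test of the number preferring Test against 50% makes no such comparison. A separate test of the order effect, as in Section 4, would leave the preference test as it was. The no-carryover argument in Section 4 concerns physiology and does not address recency of judgement.

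At stake are the power to detect a real lens preference and, if the two orders finish with unequal numbers, the accuracy of the reported share preferring Test.

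**Working it through.** **Plan figure.** The plan gives no power or sample size for preferences, so there is no figure to reproduce.

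**Inputs.** From the plan: 30 completers (Section 10.2), 5% significance and a binomial test (Section 10.3). Assumed: a two-sided test, no ties, and a last-worn share q of 50 to 80%. Here q is the proportion who would choose the last-worn pair if the lenses were equal. No document figure supports any value of q other than 50%, or excludes any.

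**Model.** With r = ln(q/(1−q)) and lens effect d on the log-odds scale:
- P(prefer Test | Test worn second) = expit(d + r)
- P(prefer Test | Test worn first) = expit(d − r)

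d = 0 is no lens difference. d = 0.85 is a 70:30 preference, since ln(0.7/0.3) = 0.847.

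**Tests compared, by exact enumeration of all outcomes.**
- Binomial: with 30 answers it rejects at 9 or fewer, or 21 or more, preferring Test.
- Mainland-Gart chi-square: compares the proportion preferring the last-worn pair between the two orders, z = (x₁ − x₂)/√[p(1−p)(1/n₁ + 1/n₂)], with p the combined proportion. It rejects at |z| ≥ 1.96.
- Fisher's exact test on the same 2×2 table.

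**Step 1: balanced orders, 15/15 (all in %).**

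| Last-worn share q | 50 | 60 | 70 | 80 |
|---|---|---|---|---|
| Size, binomial | 4.28 | 3.86 | 2.69 | 1.15 |
| Size, Mainland-Gart chi-square | 4.56 | 4.87 | 5.48 | 4.96 |
| Power, binomial | 59 | 56 | 45 | 26 |
| Power, Mainland-Gart chi-square | 60 | 59 | 55 | 45 |
| Power, Fisher's exact | 44 | 41 | 36 | 28 |

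To see why power falls, take q = 80%, so r = ln 4 = 1.386. The two probabilities are expit(2.236) = 0.903 and expit(−0.536) = 0.369, with mean 0.636. The expected count preferring Test is 30 × 0.636 = 19.1, below the rejection limit of 21, although the lens effect is still 70:30.

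**Step 2: unequal orders, no lens difference.** The expected share preferring the lens more often worn second is [n₁q + n₂(1−q)]/30. For 18/12:
- q = 60%: (10.8 + 4.8)/30 = 52%
- q = 70%: (12.6 + 3.6)/30 = 54%
- q = 80%: (14.4 + 2.4)/30 = 56%

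False-positive rate of the binomial test, given the split (%):

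| Split | q = 60 | q = 70 | q = 80 |
|---|---|---|---|
| 17/13 | 4.08 | 3.48 | 2.41 |
| 18/12 | 4.36 | 4.51 | 4.30 |
| 19/11 | 4.75 | 6.02 | 7.49 |
| 20/10 | 5.26 | 8.07 | 12.37 |

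At 20/10 the Mainland-Gart chi-square gives 5.0/4.7/3.7%.

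**Step 3: how likely are such splits?** Under simple 1:1 randomisation of 30, 19/11 or worse has probability 20% and 20/10 or worse 10%. If 40 are allocated 20/20 and 10 are lost independently of order, 20/10 has probability 2 × C(20,10)/C(40,10) = 0.04%, and 19/11 or worse 0.8%.

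**Step 4: average over 1:1 randomisation.** With no lens difference each wearer's chance of preferring Test is ½q + ½(1−q) = ½, whatever q is. The pooled count is then Binomial(30, ½) and the size is 4.3%.

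**The case against.** **The text is permissive.** Section 10.3 says only that binomial tests may be used, refers to the study design, and sits alongside a promised order test. A reader might infer that the plan commits to a pooled analysis ignoring order. The documents do not say that; pooling is the natural reading of a binomial test with no order term, but it is an inference. What stands is that no method using order is named for preferences.

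**The false-positive argument is limited.** A reader might infer that 50% is the wrong null value unless the orders are equal, or that the error rate is generally 8 to 12%. Steps 2 to 4 do not support either. Inflation is conditional on a split of about 19/11 or worse together with a sizeable last-worn effect. It does not arise on average under 1:1 randomisation. Overall inflation would need a systematic imbalance, such as dropout related to order, and the documents suggest none. Whether allocation is blocked cannot be seen.

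**The better test is not free in every form.** Fisher's exact version at 15/15 has 44% power against 59% for the binomial when there is no order effect, and overtakes it only at about q = 80%. The chi-square form is approximate. This stands and shapes the fix.

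**The premise is unseen.** No last-worn effect is documented, and the preference question itself is not visible. The objective preferences mentioned in Section 10.3 are not shown to rest on the wearer's recall, so the argument is confined to wearers' own preferences.

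**Conclusion.** The point holds as a low-importance improvement. The one test named for preferences cannot use the randomised wearing order, and the order test in Section 4 would not correct it.

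The main consequence is lost power, and it needs no imbalance. With 30 answers at 15/15 and a 70:30 lens effect, the binomial test falls behind the order-stratified chi-square by about 10 points at a last-worn share of 70% and 19 points at 80%. At 50% the two are within a point. With unequal orders, the reported share also moves by 2 to 6 points at 18/12 for shares of 60 to 80%, given that split.

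These sizes rest on assumed last-worn shares, forced-choice answers, a two-sided test and lens and order effects that add on the log-odds scale. The evidence does not support a claim that the preference test has an inflated false-positive rate in general. No sample size or named endpoint depends on preference.

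**What to change.** In Section 10.3, replace the binomial sentence, as far as it concerns wearers' preferences, with wording such as:

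> *Wearers' preferences will be analysed by randomised lens order. Order will be cross-tabulated against preferred pair (first or second). Lens preference will be tested with the Mainland-Gart test in its chi-square form, or Prescott's test if no preference is an allowed answer. The Test preference will be reported as the unweighted mean of the two order-specific proportions with a 95% confidence interval. The overall first-versus-second-pair preference will be reported as the order effect referred to in Section 4.*

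**Cost.** A short change of wording and a 2×2 (or 2×3) table in place of a one-sample test. Order is known from the randomisation schedule and the preferred pair is the answer itself, so no extra data, visits or participants are needed.

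**Downsides to accept.** The chi-square form is approximate: its size reaches about 5.5% at 15/15 and about 6% at 5/5, which matters if only the minimum of 10 complete. At 20/10 with no order effect it costs about 1 point of power (59% to 58%). Fisher's exact form should not be the default, because of its power loss at 15/15.
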